
Exclusion:

Age < 18

Conversion to open surgery

Acute cholecystitis

Prior common bile duct surgery

Presence of diastasis recti or umbilical hernia

4. Surgical Technique

Standard LC using:

10 mm umbilical camera port

10 mm epigastric port

Two 5 mm subcostal ports

Fascial closure was performed only at the umbilical site using polyglactin sutures.

Epigastric port sites were not sutured.

Gallbladder retrieval performed using a bag.

5. Postoperative Management & Follow-Up

Pain Control:

IV paracetamol and tramadol postoperatively. VAS recorded at 6 and 24 hours.

Discharge & Follow-up:

Routine discharge on Day 1 if no complications. All patients followed for 12 months.

Hernia Diagnosis:

Symptomatic patients evaluated with ultrasonography. Asymptomatic patients underwent

scheduled USG at 6 and 12 months.

6. Statistical Analysis

- Data analyzed with SPSS v26 and RStudio.
- Categorical data were analyzed using Fisher's exact or Chi-square tests
- Continuous variables were compared using Student's t-test or Mann–Whitney U test
- Univariate and multivariate logistic regression performed to evaluate TSH risk factors.
- Significance threshold: P < 0.05

7. Results Summary

Demographics:

Age, BMI, and other baseline factors were comparable between groups.

Outcomes:

- Hernia rate: 6 in Group U, 5 in Group E (all at umbilicus)
- Retrieval time shorter in Group E (P = 0.013)
- Pain lower in Group U at 6h (P = 0.027)
- No difference in 24h VAS scores
- Multivariate Analysis:
- Fascial widening was the only independent predictor of TSH (OR = 4.08, P = 0.05)

8. Discussion

- All trocar site hernias (TSH) occurred at the umbilical site, regardless of extraction route.
- This confirms the umbilicus as the most vulnerable location for hernia development after
- laparoscopic cholecystectomy.
- Epigastric extraction avoided direct stress on the umbilical site and was associated with no
- hernias at the epigastric port.
- Gallbladder retrieval was faster via the epigastric route, offering operative efficiency.
- Early postoperative pain (6h) was slightly higher with epigastric extraction but not clinically
- limiting.
- Fascial widening during extraction was the only independent risk factor for TSH.
- These findings support preferential use of the epigastric port for specimen retrieval to
- minimize hernia risk.

9. Conclusion

While trocar site selection did not statistically alter the incidence of hernia, all hernias occurred at

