the umbilicus, highlighting its vulnerability. Fascial widening during extraction was a key

modifiable risk factor. Epigastric retrieval may offer operative efficiency, but at a slight cost in

postoperative discomfort.

10. Ethical Considerations

- Approved by the Clinical Research Ethics Committee of Istanbul University of Health
- Sciences, Umraniye Training and Research Hospital.
- All participants provided written informed consent.
- Study conducted in accordance with the Declaration of Helsinki.
- No funding received. No conflicts of interest declared.

STATISTICAL ANALYSIS PLAN (SAP)

Study Title: Umbilical Trocar Site Is the Usual Suspect for Trocar Site Hernia After

Laparoscopic Cholecystectomy: A Prospective Study

Version: 1.0

Prepared by: [name]

Study Sponsor: Umraniye Research and Training Hospital

Principal Investigator: Ass. [name]. [name]

1. Study Overview

This is a prospective, randomized, controlled clinical trial evaluating the incidence of trocar site hernia (TSH) in patients undergoing laparoscopic cholecystectomy, comparing gallbladder extraction via the umbilical versus epigastric port.

2. Study Objectives

Primary Objective:

To assess whether the site of gallbladder retrieval (umbilical vs. epigastric trocar) affects the incidence of trocar site hernia.

Secondary Objectives:

To compare postoperative pain levels at 6 and 24 hours between groups

To assess gallbladder retrieval time

To identify independent risk factors for the development of trocar site hernia

3. Endpoints

Primary Endpoint:

Incidence of trocar site hernia (clinical or ultrasonographic diagnosis within 12 months)

Secondary Endpoints:

- Gallbladder retrieval time (in seconds)
- Visual Analogue Scale (VAS) pain scores at 6 and 24 hours postoperatively
- Occurrence of fascial widening and its association with TSH

• Logistic regression model identifying independent risk factors for TSH

4. Analysis Populations

Intention-to-Treat (ITT):

All randomized patients, excluding those who converted to open surgery or were lost to follow-

up.

Per Protocol (PP):

Patients who completed surgery and 12-month follow-up without major protocol deviations.

5. General Statistical Methods

- Statistical significance threshold set at P < 0.05 (two-sided).
- All statistical analyses will be performed using SPSS v26.0 and RStudio v4.2.0.
- Results will be reported with appropriate confidence intervals (CIs) and effect sizes when
- applicable.

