6. Data Handling and Assumptions

Missing Data:

No imputation will be performed.

Patients lost to follow-up will be excluded from analysis of outcomes they did not complete.

Outliers:

Checked visually (boxplots, scatterplots).

No exclusions unless clinically justified.

Normality Testing:

Shapiro-Wilk test used for continuous variables.

7. Baseline and Demographic Comparisons

Descriptive statistics: mean ± SD for normally distributed data; median (min-max) for non-

normal data; frequency (%) for categorical variables.

Comparisons:

• Categorical variables: Chi-square or Fisher's exact test

• Continuous variables: Student's t-test or Mann–Whitney U test depending on distribution

8. Primary Endpoint Analysis

Incidence of TSH:

Compared between the umbilical and epigastric groups using Fisher's exact test.

9. Secondary Endpoint Analyses

- Gallbladder retrieval time: Compared using Mann–Whitney U test (non-normal distribution
- anticipated).
- Postoperative pain scores (VAS at 6h and 24h): Assessed separately at both time points.
- Compared using Mann–Whitney U test.
- Exploratory regression analyses: Univariate logistic regression to identify factors associated
- with TSH Variables with P < 0.2 or known clinical relevance will be entered into a
- multivariate logistic regression model.
- Odds Ratios (OR), 95% CI, and P-values will be reported.

10. Subgroup Analyses

Subgroup analysis will be performed for patients in the umbilical extraction group to evaluate the

impact of fascial widening on TSH incidence using logistic regression.

11. Software

All analyses will be conducted using:

- SPSS v26.0 (IBM Corp., Armonk, NY, USA)
- RStudio v4.2.0 (The R Foundation)

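### The CSR's hernia-risk case for epigastric retrieval, and its causal reading of fascial widening (OR 4.08, P = 0.05), go further than the reported data allow

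*Combined protocol and SAP*

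**What the plan says.** **Retrieval route.** CSR section 7 reports "Hernia rate: 6 in Group U, 5 in Group E (all at umbilicus"; the synopsis gives these as 6/50 and 5/50 with P = 1.00. CSR section 8 says "These findings support preferential use of the epigastric port for specimen retrieval to" minimize hernia risk. CSR section 9 says "While trocar site selection did not statistically alter the incidence of hernia, all hernias occurred at" the umbilicus.

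**Fascial widening.** Under the label Multivariate Analysis, CSR section 7 reports "Fascial widening was the only independent predictor of TSH (OR = 4.08, P = 0.05". Section 8 repeats this as "Fascial widening during extraction was the only independent risk factor for TSH", and section 9 as "Fascial widening during extraction was a key" modifiable risk factor.

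**What was planned.** SAP section 9 describes the univariate and multivariate logistic regressions as exploratory and says "Odds Ratios (OR), 95% CI, and P-values will be reported". SAP section 10 plans a separate logistic regression of hernia on widening within the umbilical extraction group. SAP section 5 sets significance at P < 0.05, two-sided. CSR section 4 shows that every patient had a "10 mm umbilical camera port", whichever port was used for extraction.

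**What is not stated.** The documents do not give the port at which widening was recorded, the number of patients with widening in either arm, the covariates in the model, a CI for the odds ratio, or any result labelled as the SAP section 10 analysis.

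**The concern.** Two statements in the CSR are stronger than their evidence.

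First, the Discussion draws a hernia advantage for one route from a trial whose randomized comparison of routes demonstrated no difference. The Conclusion of the same report says as much.

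Second, an exploratory odds ratio becomes a causal claim: independent, modifiable, and arising during extraction. Widening occurs after allocation and was not randomized, and the model rests on 11 events. What the odds ratio means also depends on the port. If the widened port and the herniated port differ in some patients, it does not measure what the wording says.

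At stake is whether readers take from this trial a preventable cause of hernia, and a hernia benefit of one route, that it has not established. The primary analysis itself is not affected.

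**Working it through.** **1. Primary comparison.** Inputs: 6/50 and 5/50 (CSR synopsis); Fisher's exact test (SAP section 8). With equal arms and 11 events, 6 v 5 is the most even split possible, so the two-sided Fisher P is 1.00. The printed value is reproduced.

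- Risk difference, umbilical minus epigastric: 12% - 10% = 2.0 percentage points.
- Wilson 95% limits: 5.6% to 23.8% for 6/50; 4.4% to 21.4% for 5/50.
- Newcombe lower limit: 0.020 - √[(0.120 - 0.0562)² + (0.2136 - 0.100)²] = -0.110.
- Newcombe upper limit: 0.020 + √[(0.2381 - 0.120)² + (0.100 - 0.0435)²] = +0.151.
- Risk ratio, epigastric to umbilical: 0.10/0.12 = 0.83. SE of the log = √(1/5 - 1/50 + 1/6 - 1/50) = 0.572; 95% CI exp(-0.182 ± 1.96 × 0.572) = 0.27 to 2.55.

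The interval is compatible with a sizeable effect in either direction.

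**2. The missing CI.** Inputs: OR 4.08, P = 0.05 (CSR section 7), assuming a Wald test. ln 4.08 = 1.406.

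| P before rounding | SE = 1.406/z | 95% CI |
|---|---|---|
| 0.045 | 0.701 | 1.03 to 16.1 |
| 0.050 | 0.717 | 1.00 to 16.6 |
| 0.055 | 0.733 | 0.97 to 17.2 |

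The printed figure leaves open which side of the threshold the result falls on.

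**3. Which patients gave the odds ratio.** The Multivariate Analysis label and the 100 patients in the final analysis already point to the SAP section 9 model in both arms. As a check, suppose widening is yes/no and take crude 2×2 tables. In Group U, with 6 hernias, the two event cells alone contribute at least 1/3 + 1/3 to the variance. SE therefore exceeds √0.667 = 0.816, and an OR of 4.08 would have z below 1.406/0.816 = 1.72 and P above 0.085. That does not round to 0.05. With 11 hernias in 100 patients, suitable tables exist:

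- 4/15 v 7/85: OR = (4 × 78)/(11 × 7) = 4.05, Wald P = 0.047.
- 8/43 v 3/57: OR = (8 × 54)/(35 × 3) = 4.11, Wald P = 0.047.

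These are the only two pooled tables with OR 4.03 to 4.13 and a Wald P that rounds to 0.05. They have 15 and 43 widened patients, so the number with widening cannot be recovered.

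**4. What a pooled odds ratio would mean.** Five of the 11 hernias (45%) were umbilical hernias in patients whose gallbladder left through the epigastric port.

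- If widening was recorded at the extraction port, epigastric widening is set against umbilical hernia in Group E.
- If umbilical widening was recorded in everyone, the sites match, but in Group E the widening did not arise from extraction.
- If it was umbilical, recorded only in Group U, and arm was in the model, the estimate is that of Group U, which step 3 finds does not fit (ignoring other covariates).

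None of these yields a pooled estimate of extraction widening on hernia at the same port.

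**5. What the planned Group U analysis can deliver.** At OR 4.08, precision is best with 3 of the 6 hernias in widened patients. The 44 non-hernia patients then split 8.66 to 35.34, and SE = √(1/3 + 1/3 + 1/8.66 + 1/35.34) = 0.900. The 95% CI is exp(1.406 ± 1.96 × 0.900) = 0.70 to 23.8.

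**The case against.** The report does not hide its primary result: the synopsis lists 6/50 v 5/50, P = 1.00 first among its key results. The Conclusion claims only operative efficiency for the epigastric route, at some cost in discomfort, and the hernia-risk statement is a single Discussion bullet that follows other findings. The origin of the odds ratio is also less obscure than it may seem, since only SAP section 9 plans a multivariate model. The rest is incomplete reporting of a secondary analysis. All of this is fair, and it limits the weight of the point. It does not remove the conflict between CSR sections 8 and 9, the omitted CI, or the causal wording, which the Conclusion repeats.

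A reader might also infer more than the documents support:

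- *That the trial shows retrieval route has no effect on hernia.* The interval of -11.0 to +15.1 points is far too wide for that.
- *That the odds ratio is proven to be pooled, or that the SAP section 10 analysis was not done.* The table check applies crude tables to an adjusted estimate and assumes binary widening. It supports an inference only, and an unlabelled result is not evidence of an analysis not run.
- *That widening is unrelated to hernia, or that the odds ratio is biased in a known direction.* Without port, counts and covariates, neither can be said.
- *That the route recommendation is clinically wrong.* The point is only that its hernia-risk ground and the reported comparison do not agree.

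**Conclusion.** The point holds as a matter of interpretation and reporting, and should be corrected. The randomized data demonstrate no difference in hernia between routes, so the section 8 hernia-risk statement lacks support from the comparison designed to test it.

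The widening result is an exploratory association from 11 events. Its implied lower confidence limit lies between 0.97 and 1.03, and the port is unstated. The words independent, modifiable and during extraction are not established by what is reported.

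The implied CI assumes a Wald test. The attribution to all 100 patients rests mainly on the CSR's own label, with the crude-table check as support. The conflict between CSR sections 8 and 9, the missing CI and the unstated port depend on neither assumption.

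**What to change.** - Reconcile the hernia-risk statement in CSR section 8 with section 9 and the primary result. Report the risk difference with its 95% CI beside the Fisher P, worded as no difference demonstrated and not as equivalence.
- Describe the widening odds ratio as an exploratory association. Give its 95% CI, unrounded P, analysis set, covariates, the port at which widening was recorded, and widening and hernia counts by arm. If the port was not recorded in Group E, state that as a limitation.
- Withdraw the terms independent, key modifiable and during extraction unless site-matched data support them.
- Report the SAP section 10 Group U logistic regression as planned, with its 95% CI, labelled exploratory. Add Fisher's exact test or Firth regression as a sensitivity analysis, given 6 events. This subgroup should not become the sole basis for any statement about widening.

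The cost is rewording, one definition and a short re-analysis of data already collected; no new patients are needed. In Group U the extraction port is the umbilical port, so that analysis needs no extra port information. The downside is that the widening finding will look less definite and the Group U estimate will be very imprecise.

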Study Title: Umbilical Trocar Site Is the Usual Suspect for Trocar Hernia After LaparoscopicCholecystectomy: A Prospective StudyNCT ID: Not yet assigned.

Date: April 15, 2025

CLINICAL STUDY REPORT (CSR)

Study Title: Umbilical Trocar Site Is the Usual Suspect for Trocar Hernia After Laparoscopic
Cholecystectomy: A Prospective Study
Study Type: Prospective, randomized controlled trial
Study Duration: April 15, 2022 – June 15, 2024
Study Location: Umraniye Training and Research Hospital, Department of General Surgery
Principal Investigator: Ass. [name]. [name]
ClinicalTrials.gov ID: Not yet assigned

1. Study Synopsis

Objective:

To evaluate whether the site of gallbladder retrieval (umbilical vs. epigastric) affects the incidence of trocar site hernia (TSH) following laparoscopic cholecystectomy (LC), and to identify risk factors for TSH.

Design:

Prospective, randomized, single-blind, controlled study with two parallel arms.

Participants:

110 patients undergoing elective LC for gallstone disease were randomized. After accounting for conversions and loss to follow-up, 100 patients (50 in each group) were included in the final analysis.

Intervention:

Standard 4-port LC performed. Gallbladder retrieved via either:

Group U: Umbilical trocar (10 mm)

Group E: Epigastric trocar (10 mm)

Primary Outcome:

Incidence of trocar site hernia at 12-month follow-up.

Secondary Outcomes:

Gallbladder retrieval time

Postoperative pain scores (VAS at 6 and 24 hours)

Risk factor analysis for TSH development

Key Results:

TSH occurred in 12% (6/50) of umbilical group and 10% (5/50) of epigastric group (P = 1.00).

All hernias were located at the umbilical site.

Epigastric retrieval was faster (P = 0.013) but associated with more early pain (P = 0.027).

Fascial widening was the only independent risk factor for TSH (OR = 4.08, P = 0.05).

2. Study Design

Randomization:

Performed via the Alea Randomisation mobile app. Allocation was sealed and revealed intraoperatively before specimen retrieval.

Blinding:

Patients were blinded. Surgeons were not blinded due to the nature of the procedure, but were unaware of group allocation until extraction.

Surgeon Consistency:

All surgeries were performed by three experienced general surgeons using standardized techniques.

Antibiotic Prophylaxis:

Intravenous cefazolin 2 g administered preoperatively.

3. Inclusion / Exclusion Criteria

Inclusion:

Age ≥ 18

Gallstone disease

No significant systemic comorbidities

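### CSR Section 8 ends on a hernia-prevention inference for epigastric retrieval that the randomised result (6/50 v 5/50, P = 1.00) does not support and that Section 9 does not draw

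*Combined protocol and SAP*

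**What the plan says.** The primary objective (SAP Section 2) is whether retrieval site affects the incidence of trocar site hernia. SAP Section 8 compares the arms with Fisher's exact test.

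- **Result.** CSR Section 1: "TSH occurred in 12% (6/50) of umbilical group and 10% (5/50) of epigastric group (P = 1.00"). CSR Section 7 adds the location: "Hernia rate: 6 in Group U, 5 in Group E (all at umbilicus").
- **Analysed set.** 110 patients were randomised. "After accounting for conversions and loss to follow-up, 100 patients (50 in each group) were included in the final analysis".
- **Discussion.** CSR Section 8 ends with "These findings support preferential use of the epigastric port for specimen retrieval to", and the sentence goes on to give reduction of hernia risk as the aim. An earlier point in the same list says "Epigastric extraction avoided direct stress on the umbilical site and was associated with no" hernias at the epigastric port.
- **Closure.** CSR Section 4: "Fascial closure was performed only at the umbilical site using polyglactin sutures".
- **Widening.** CSR Section 7: "Fascial widening was the only independent predictor of TSH (OR = 4.08, P = 0.05"). The threshold in CSR Section 6 is "Significance threshold: P < 0.05". SAP Section 9 labels the regression exploratory and says the odds ratio will come with a 95% CI and a P value.
- **Conclusion.** CSR Section 9 says that site made no statistical difference to hernia incidence. It credits epigastric retrieval with possible efficiency, at some cost in discomfort. It also calls fascial widening modifiable.

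**The concern.** The report gives two readings of its own primary question. Sections 1, 7 and 9 present a null result, while Section 8 ends by offering a route of retrieval as a way to reduce hernia. A reader who takes the message from the Discussion leaves with a preventive claim that the randomised comparison does not support.

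The phrase about the findings could refer to the other points in Section 8 rather than to the primary comparison, so each of those needs checking as well. Section 9 omits the epigastric recommendation, but by calling widening modifiable it carries part of the same preventive reading into the Conclusion.

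**Working it through.** **1. Reproduce the printed result.** Inputs (CSR Sections 1 and 7): umbilical arm U 6/50, epigastric arm E 5/50. Two-sided Fisher's exact test on 6/44 v 5/45 gives P = 1.00, as printed. With 6/50 in U, arm E would have needed 0/50 to reach P < 0.05 (0/50: P = 0.027; 1/50: P = 0.11).

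**2. Size of the difference.** Risk difference U minus E = 12.0 - 10.0 = +2.0 points, which is one patient in 50.

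- Wilson 95% limits: U 5.62% to 23.80%; E 4.35% to 21.36%.
- Newcombe lower limit: 2.0 - sqrt[(12.0 - 5.62)² + (21.36 - 10.0)²] = 2.0 - 13.0 = -11.0.
- Newcombe upper limit: 2.0 + sqrt[(23.80 - 12.0)² + (10.0 - 4.35)²] = 2.0 + 13.1 = +15.1.

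The choice of interval matters little: the score method gives -10.9 to +15.2 and Wald gives -10.3 to +14.3. The data are compatible with anything from 11 points fewer to 15 points more hernias with umbilical retrieval. All of this applies to the 100 of 110 randomised patients who were analysed.

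**3. Do the other Section 8 points supply the support?**

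- *Direct stress on the umbilicus avoided.* This describes the procedure in arm E. Even so, 5/50 patients there (10.0%, Wilson 4.3% to 21.4%) had an umbilical hernia, against 6/50 (12.0%, 5.6% to 23.8%) in arm U.
- *No hernias at the epigastric port.* All 11 hernias were umbilical, so this holds in both arms and cannot separate the routes. The contrast between ports is also mixed with closure, since only the umbilical site was sutured.
- *Fascial widening.* This was not randomised. A whole-cohort model rests on 6 + 5 = 11 events. No widening counts by arm are printed, so nothing shows that one route produced less of it.

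**4. Precision of the widening estimate.** Assume a Wald test, so that SE = ln(OR)/z, with ln(4.08) = 1.406 and 95% CI = exp(1.406 ± 1.960 × SE). A printed 0.05 covers roughly 0.045 to 0.055.

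| P | z | SE | 95% CI for the OR |
|---|---|---|---|
| 0.045 | 2.005 | 0.701 | 1.03 to 16.1 |
| 0.050 | 1.960 | 0.717 | 1.00 to 16.6 |
| 0.055 | 1.919 | 0.733 | 0.97 to 17.2 |

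The lower limit falls on either side of 1 depending on rounding. The printed value does not show whether the P < 0.05 criterion was met.

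**The case against.** The strongest reply is that the report already discloses the null result. Sections 1 and 7 print it, the Conclusion opens with it, and the first point of Section 8 itself says location did not depend on route. The overclaim is one sentence, and no count, endpoint or analysis changes. This is true and limits the harm, but disclosure elsewhere does not correct an affirmative statement that closes the Discussion.

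Several narrower objections carry some weight:

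- *Closure.* If suturing is meant to reduce hernia, closing only the umbilicus would understate that site's vulnerability. The confounding therefore does not weaken the authors' statement about location. The sufficient answer is that location does not separate the arms.
- *Number of events.* Section 7 does not state the population of the multivariate model. The whole cohort is the natural reading under SAP Section 9, but SAP Section 10 also plans a widening regression in the umbilical arm alone, which had 6 events.
- *Port of widening.* The documents do not say at which port widening was recorded. Counts by arm would be more useful with the port stated.
- *Choice of interval.* SAP Section 5 asks for confidence intervals where applicable and names no method. Newcombe is a reasonable choice, not a requirement.

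One could also argue that epigastric retrieval spares the umbilical fascia from widening and so must help. Any net effect of route through widening is already contained in the randomised comparison, and that comparison is 6 v 5.

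**Conclusion.** The concern holds: the closing sentence of Section 8 is not supported by the trial's primary comparison or by the other points listed with it. The arms differ by one patient, and the interval of -11.0 to +15.1 points is wide in both directions. The correct reading is no evidence of a difference, with neither superiority nor equivalence shown.

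The umbilical location of all hernias is a descriptive finding common to both arms. The widening result is an imprecise, non-randomised association of borderline significance. Its reconstructed interval assumes a Wald test, and the figure of 11 events assumes a whole-cohort model. The primary-endpoint figures depend on neither assumption, but they cover only the analysed patients.

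This should be fixed. It is not graver than that, because Sections 1, 7 and 9 state the null result.

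**What to change.** Reconcile Section 8 with Sections 1, 7 and 9:

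- Remove the hernia-risk inference from the end of Section 8. State that no evidence of a difference was found and that the trial shows neither superiority nor equivalence.
- Beside the Fisher P, report the risk difference (U minus E) of +2.0 points, Newcombe 95% CI -11.0 to +15.1, in the 100 of 110 randomised patients analysed.
- Label the contrast between ports as descriptive, and note beside the point about direct stress that 5/50 patients in arm E had umbilical hernias.
- Wherever widening is used, including where Section 9 calls it modifiable, describe it as a non-randomised association. Give the 95% CI promised in SAP Section 9, P to three decimals, and widening counts by arm, preferably with the port at which it was recorded.

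The cost is text in two sections, one interval from printed counts, and regression output and widening counts that should already be held. No new test or SAP rewrite is needed. The downside is a less favourable closing statement. Nothing here says which port should be used.

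### The SAP's Intention-to-Treat set is a complete-case, non-converted set; its rule for lost patients conflicts with SAP 6, and no endpoint is assigned a population.

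*Combined protocol and SAP*

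**What the plan says.** SAP 4 gives two populations. Intention-to-Treat is "All randomized patients, excluding those who converted to open surgery or were lost to" follow-up. Per Protocol is "Patients who completed surgery and 12-month follow-up without major protocol deviations"; the term for major deviations is not defined.

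SAP 6 bars imputation and gives a different rule for losses: "Patients lost to follow-up will be excluded from analysis of outcomes they did not complete".

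The analysis sections name neither population. SAP 8 says the primary endpoint is "Compared between the umbilical and epigastric groups using" Fisher's exact test. SAP 9 says of pain: "Postoperative pain scores (VAS at 6h and 24h): Assessed separately at both time points". SAP 10 mentions only the umbilical extraction group, and section 6 of the Clinical Study Report (CSR) lists tests without a population.

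The CSR synopsis reports 110 randomised and then: "After accounting for conversions and loss to follow-up, 100 patients (50 in each group) were included in the final analysis". Its key results give hernia as 6/50 and 5/50. The two significant between-arm results are given without denominators: "Epigastric retrieval was faster (P = 0.013) but associated with more early pain (P = 0.027").

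CSR 3 lists conversion to open surgery as an exclusion. CSR 2 says of the assignment: "Allocation was sealed and revealed intraoperatively before specimen retrieval".

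**The concern.** A reader who sees the ITT label expects an analysis of everyone randomised, as allocated. The plan contains none. A reader who then compares ITT with per protocol, as a check on the effect of dropout, learns nothing about it, because lost patients are absent from both sets.

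The second problem is a contradiction. Retrieval time is measured during surgery and VAS within 24 hours, so a patient lost months later can have complete data for all three measurements. SAP 6 keeps that patient for those outcomes; SAP 4 discards them. The same holds for a hernia found at the 6-month scan in a patient who is lost before month 12: the SAP 3 endpoint counts a diagnosis within 12 months, yet SAP 4 drops the patient. The documents do not show that such a case occurred.

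The early outcomes matter because retrieval time and 6 h pain are the two between-arm comparisons reported as significant, and the CSR conclusion on efficiency and discomfort rests on them.

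**Working it through.** **The two rules side by side**

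| Patient and outcome | SAP 4 (both sets) | SAP 6 |
|---|---|---|
| Lost, no hernia assessment: hernia | out | out |
| Lost later, retrieval time recorded | out | in |
| Lost later, VAS at 6 h or 24 h recorded | out | in |
| Hernia seen, then lost | out | in, if the diagnosis counts as completing the outcome |
| Converted to open surgery | out of the ITT set | not addressed |

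The rules agree only in the first row. SAP 6 is silent on conversions, so the conflict concerns lost patients only.

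**Size of the exclusions.** Inputs from the CSR synopsis: 110 randomised, 100 analysed. 110 - 100 = 10; 10/110 = 9.1%. The ten combine conversions and losses in unstated proportions, so the number touched by the conflict lies somewhere from 0 to 10.

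**The stated primary result.** Two-sided Fisher's exact test on 6/50 v 5/50 gives P = 1.00, which reproduces the reported value. The difference, umbilical minus epigastric, is 12.0% - 10.0% = +2.0 points. For the Newcombe interval, the Wilson 95% limits are 5.6% to 23.8% (6/50) and 4.3% to 21.4% (5/50):

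- lower = 2.0 - √[(12.0 - 5.6)² + (21.4 - 10.0)²] = -11.0
- upper = 2.0 + √[(23.8 - 12.0)² + (10.0 - 4.3)²] = +15.1

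(limits carried unrounded).

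**What the ten could do to it.** Assume that none of the ten has a hernia outcome. This is an upper bound on the missing information, because some may have been scanned. If u of the ten were in the umbilical arm, with h_U hernias there and h_E hernias among the other 10 - u, the difference is (6 + h_U)/(50 + u) - (5 + h_E)/(60 - u).

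| Assumption | Umbilical v epigastric | Difference (points) | Fisher P |
|---|---|---|---|
| 55/55, all five epigastric removals had a hernia | 6/55 v 10/55 | 10.9 - 18.2 = -7.3 | 0.418 |
| 55/55, all five umbilical removals had a hernia | 11/55 v 5/55 | 20.0 - 9.1 = +10.9 | 0.175 |
| All ten epigastric, all with a hernia | 6/50 v 15/60 | 12.0 - 25.0 = -13.0 | 0.095 |
| All ten umbilical, all with a hernia | 16/60 v 5/50 | 26.7 - 10.0 = +16.7 | 0.030 |

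The equal split is an assumption; the documents give only the analysed 50 per arm. Its two extremes lie inside the complete-case interval, whereas the all-splits extremes lie just outside it at both ends. Letting u, h_U and h_E take every possible value gives 286 configurations. Three have P < 0.05: 15/59 v 5/51 (P = 0.047), 15/60 v 5/50 (P = 0.0496) and 16/60 v 5/50 (P = 0.030). Each needs at least nine of the ten in the umbilical arm and at least nine hernias among the ten, against 11 hernias in the 100 analysed.

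**Retrieval time and VAS.** No distributions, denominators or counts of affected patients are given, so no recalculation of P = 0.013 or P = 0.027 is possible.

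**The case against.** The strongest defence has four parts.

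- **Conversion is a listed exclusion, and the allocation was revealed late.** A conversion before the reveal could not depend on knowing the allocation. This stands and limits the bias from removing such patients. It does not cover conversions after the reveal or losses, and it does not make the set ITT.
- **The exclusions are disclosed, and the primary set is visible.** Also true: the synopsis names both reasons, and 6/50 and 5/50 match the 100 analysed. What is missing is counts by reason and arm, and denominators for retrieval time and VAS.
- **No changed result is shown.** This is fair. A reader might infer that the two significant P values are unsafe, or that all ten patients are caught by the rule conflict. The documents support neither: the effect on those P values is unknown, and only lost patients with early data, or with a hernia seen before the loss, are affected.
- **The SAP 4 rule was evidently used throughout.** The figure of 100 suggests so, but the CSR does not call its 100 patients ITT and does not state the set for each endpoint. The link is an inference from matching exclusions.

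These points limit the consequence. The wrong label and the contradiction between SAP 4 and SAP 6 remain.

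**Conclusion.** The point holds and should be fixed. The text is wrong as written, beyond any lack of detail: followed literally, SAP 4 discards observed data that SAP 6 says to keep.

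For the primary endpoint it is a labelling and reporting defect. A reader might infer that removing 9.1% of patients, nearly as many as there were hernias, puts the null result in doubt. It does not: significance needs an extreme one-sided pattern, and no configuration under an equal split has a P value below 0.175. What the removals do affect is precision, since the possible difference runs from -13.0 to +16.7 points if the arm split is left open and all ten are taken as unassessed.

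For retrieval time and VAS, the analysed set is ambiguous and the consequence cannot be sized from the documents.

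**What to change.** 1. Rename the SAP 4 set complete-case (non-converted) and stop calling it ITT. Redefining ITT as all 110 would not by itself give a primary estimate, because SAP 6 bars imputation.
2. Reconcile SAP 4 with SAP 6 by applying the outcome-by-outcome rule. Analyse retrieval time and VAS, as allocated, in all non-converted randomised patients with those data, including those later lost. Show converted patients separately, or add them for VAS as a sensitivity analysis. State population and denominator for each endpoint in SAP 8 and 9.
3. For hernia, add a sensitivity analysis that includes lost patients with any scan, both those with a hernia and those hernia-free at last scan. Adding only the events would push the incidence up selectively.
4. Report the ten exclusions by arm and reason, with conversions split into before and after the allocation reveal.
5. Give the best/worst-case bound above with the actual arm split.

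Label every redefinition and re-run post hoc, because the SAP is filed together with the results.

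The cost is wording in the SAP and CSR, one table and a short re-run. The bound needs only the exclusions by arm. The early-outcome re-run is possible only if those data were kept, which the documents do not say. The downside is a wider reported range for the primary result.
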